### 9.3.3. Endpoints of Interest

The endpoints of interest captured in the semi-annual reports are the following safety events of interest.

For the interim feasibility analysis and final safety report (where also information on patients, co-variates and outcomes, from SRQ as well as from the linked Patient/Prescribed Drug and other registers will be included) of pre-specified safety outcomes, the following events of interest have been pre-specified.

1. Hospitalized infections overall.
2. Opportunistic infections.
3. Herpes zoster (hospitalized).

090177e199570500\Approved\Approved On: 13-Feb-2022 20:25 (GMT)

4. Hepatitis.
5. Fractures.
6. NMSC.
7. Malignancies (overall, excluding NMSC).
8. Lung Cancer.
9. Lymphoma (overall and independently by subtype, including non-Hodgkin lymphoma, Hodgkin lymphoma, and chronic lymphatic leukemia).
10. CV events, including deep vein thrombosis/pulmonary embolism (DVT/PE).
11. Major Adverse Cardiovascular Events (MACE).
12. Myocardial infarction (MI)
13. Gastrointestinal (GI) perforations.
14. Progressive multifocal leukoencephalopathy (PML).
15. Interstitial lung disease, pending feasibility.
16. All-cause Mortality.

Given the age-dependent rate events of interest, analysis will be conducted in elderly patents aged  $\geq 65$  years.

This list may be extended with a reasonable number of additional sub-diagnoses or new health related outcomes as agreed to by ARTIS researchers and Sponsor before the interim feasibility analysis and final safety report. These decisions will be made prior to initiation of analyses and documented in a statistical analysis plan (SAP) kept on file by the Sponsor.

In addition, the final safety reports will include the number of tofacitinib-exposed pregnancies.

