### **9.7.2. Final Safety Report**

The feasibility of conducting a final comparative study will be evaluated at an interim time point and at 7-years of follow up based on statistical power and suitable overlap in patient populations in the exposure groups. The feasibility assessment, like the final report, will be conducted using safety events of interest identified through linkages with the patient, cancer and death registers, as appropriate. ARTIS will apply an ICD-code based algorithm to identify serious infections, GI perforations, herpes zoster, and CV events (MACE), in the Swedish patient register. Appendix 4 describes the algorithms used to identify these endpoints in ARTIS and relevant validation references, along with definitions used by other EU registers. The specific algorithms for defining those endpoints have not been validated, though the Swedish patient register has been validated several times (Ludvigsson 2011). The overall positive predictive value (PPV) of the inpatient diagnoses generally ranged from 85% to 95%. A regional validation study of hospitalized acute MI and stroke (components of the MACE endpoint) found positive predictive values of 96% and 94% respectively, in the period 1977 to 1987 (Lindblad, 1993). An ICD-9 code based algorithm applied to inpatient diagnoses of GI perforations in the US demonstrated high PPV (89.1-100) (Curtis, 2011). While the ICD algorithms used by ARTIS to define the endpoints of interest may not be validated, their use can be justified given the importance to contextualize the study results with historical findings. ARTIS has previously conducted and published studies of serious infections (Askling, 2007), PML (Arkema, 2012), and MACE (Michaud, 2016) events in RA patients.

The Swedish national register for contagious diseases, will serve as source of information on TB and other possibly serious contagious diseases for which there is a mandatory registration in Sweden. These reports will be based on a standardized analytical scheme, with some but limited flexibility to add additional endpoints and stratification, and will contain populated tables in line with the shells in Appendix 2. Whether these reports include formal comparisons of patients exposed to tofacitinib and bDMARDs will be determined a priori based on adequate power.

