**Appendix 4. ICD and MedDRA Codes For Select Safety Endpoints**

Event	ARTIS		BIOBADASER, BSRBR, RABBIT
	Operationalization	Validation ICD	Operationalization (Final list TBD based on reported endpoints).
Serious infections	Hospitalizations in the Patient Register listing as main diagnosis ICD10-codes below. If main diagnosis is RA, contributory diagnoses are also considered. A00-B99 (excluding A33 and A50), D73.3, E32.1, G00-G02, G04.2, G05-G07, H00.0, H44.0, H60.0-H60.3, H66-H67, H70, I30.1, I40.0, J00-J22, J32, J34.0, J36, J39.0-J39.1, J44.0, J85, J86, K04.4, K04.6, K04.7, K10.2, K11.3, K12.2, K14.0, K57.0, K57.2, K57.4, K57.8, K61, K63.0, K65.0, K65.1, K65.2, K65.9, L00-L08, L30.3, M00-M01, M46.2-M46.5, M60.0, M65.0, M71.0, M71.1, M72.6, M86, N13.6, N15.1, N15.9, N30.0 N30.8, N34.0, N41.2, N43.1, N45.2, N45.3, N45.4, N48.2, N61, N70, N73, N75.1	This algorithm has not been specifically validated in ARTIS, but the register itself is subject to strict quality assurance routines and has been validated several times. Refs: Ludvigsson et al. External Review and Validation of the Swedish National Inpatient Register, BMC Public Health, 2011 (11):450. http://www.socialstyrelsen.se/register/halsodataregister/patientregistret/inenglish .	Hospitalization and/or use of parenteral antibiotics+ MedDRA Infections and Infestations SOC 10021881.
HZ reactivation	Hospitalizations in the Patient Register listing as main diagnosis ICD10-codes B00 and B02. If main diagnosis is RA, contributory diagnoses are also considered.	The algorithm used to identify this endpoint in ARTIS has not been validated and is expected to only identify the most severe cases.	10019974 Herpes zoster, 10019983 Herpes zoster ophthalmic, 10030865 Ophthalmic herpes zoster, 10058428 Herpes zoster multi-dermatomal, 10063491 Herpes zoster oticus, 10065038 Herpes zoster disseminated, 10065119 Necrotising herpetic retinopathy, 10072210 Genital herpes zoster, 10074241 Varicella zoster gastritis, 10074245 Herpes zoster pharyngitis, 10074248 Herpes zoster meningoencephalitis, 10074253 Herpes zoster necrotising retinopathy, 10074254 Varicella zoster pneumonia, 10074254 Varicella zoster pneumonia, 10074259 Herpes zoster meningitis, 10074297 Herpes zoster cutaneous disseminated.

090177e199570500\Approved\Approved On: 13-Feb-2022 20:25 (GMT)

090177e199570500\Approved\Approved On: 13-Feb-2022 20:25 (GMT)

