GI perforation	Hospitalizations in the Patient Register listing ICD10-codes: K22.3, K25.1, K25.2, K25.5, K25.6, K26.1, K26.2, K26.5, K26.6, K27.1, K27.2, K27.5, K27.6, K28.1, K28.2, K28.5, K28.6, K31.6, K35.0, K35.1, K57.0, K57.2, K57.4, K57.8, K63.0, K63.1, K63.2.	See Serious Infections ; Pharmacoepidemiol Drug Saf. 2011 Nov;20(11):1150-8. doi: 10.1002/pds.2215. Epub 2011 Aug 27. Validation of ICD-9-CM codes to identify gastrointestinal perforation events in administrative claims data among hospitalized rheumatoid arthritis patients.		10000099 Abdominal wall abscess; 10000285 Abscess intestinal; 10000582 Acquired tracheo-oesophageal fistula; 10002156 Anal fistula; 10002157 Anal fistula excision; 10002248 Anastomotic ulcer perforation; 10002924 Aorto-duodenal fistula; 10003012 Appendicitis perforated; 10009995 Colonic fistula; 10013536 Diverticular fistula; 10013538 Diverticulitis; 10013541 Diverticulitis intestinal haemorrhagic; 10013828 Duodenal fistula; 10013832 Duodenal perforation; 10013849 Duodenal ulcer perforation; 10013849 Duodenal ulcer perforation; 10013850 Duodenal ulcer perforation, nonobstructive; 10017815 Gastric perforation; 10017835 Gastric ulcer perforation; 10017836 Gastric ulcer perforation, obstructive; 10017866 Gastritis haemorrhagic; 10017877 Gastrointestinal fistula; 10017954 Gastrointestinal gangrene; 10017955 Gastrointestinal haemorrhage; 10018001 Gastrointestinal perforation; 10021305 Ileal perforation; 10021310 Ileal ulcer perforation; 10022647 Intestinal fistula; 10022694 Intestinal perforation; 10023174 Jejunal perforation; 10023178 Jejunal ulcer perforation; 10023804 Large intestine perforation; 10030181 Oesophageal perforation; 10034354 Peptic ulcer perforation; 10034358 Peptic ulcer perforation, obstructive; 10034397 Perforated peptic ulcer oversewing; 10034649 Peritoneal abscess; 10034674 Peritonitis; 10038073 Rectal perforation; 10038975 Retroperitoneal abscess; 10041103 Small intestinal perforation; 10046274 Upper gastrointestinal haemorrhage; 10048946 Anal abscess; 10048947 Rectal abscess; 10049583 Douglas' abscess; 10049764 Appendiceal abscess; 10050362 Anovulvar fistula;	

090177e199570500\Approved\Approved On: 13-Feb-2022 20:25 (GMT)

	ARTIS		BIOBADASER, BSRBR, RABBIT
Event	Operationalization	Validation ICD	Operationalization (Final list TBD based on reported endpoints).

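### The Appendix 4 list for GI perforation includes fistula and abscess codes and sets no diagnosis-position or incident-event rule, so the endpoint does not measure perforation alone

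*Protocol*

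**What the plan says.** Section 9.3.3 of the protocol names the endpoint as "Gastrointestinal (GI) perforations". Section 9.3.2 places it among the outcomes counted from drug start to 90 days after the end of treatment.

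Section 9.7.2 says that ARTIS will identify it with an ICD-code algorithm and points to Appendix 4. The ARTIS column there begins "Hospitalizations in the Patient Register listing ICD10-codes: K22.3, K25.1, K25.2" and ends with "K31.6, K35.0, K35.1, K57.0, K57.2, K57.4, K57.8, K63.0, K63.1, K63.2". It says nothing on whether the code must be the main diagnosis, and nothing on patients who already had such a code before index.

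Two other rows of the same table do limit the position. Serious infection reads "Hospitalizations in the Patient Register listing as main diagnosis ICD10-codes below". Herpes zoster reads "Hospitalizations in the Patient Register listing as main diagnosis ICD10-codes B00 and B02". Both admit contributory diagnoses only when the main diagnosis is RA.

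On validity, Section 9.7.2 states that the ARTIS algorithms themselves are not validated. It quotes a general inpatient PPV of 85% to 95% for the register, and for this endpoint adds: "An ICD-9 code based algorithm applied to inpatient diagnoses of GI perforations in the US demonstrated high PPV (89.1-100" (per cent). The same section leaves an ICD algorithm harmonised with the other registers to the final SAP.

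**The concern.** The name of the endpoint and its code list do not match. Under standard ICD-10 labels, perforation of the intestine has its own code, K63.1. The list also takes in K63.0 (abscess of intestine), K63.2 (fistula of intestine) and K31.6 (fistula of stomach and duodenum).

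A fistula can be long-standing. With no position limit and no look-back rule, a fistula present before the drug was started and recorded as a secondary diagnosis at any later admission meets the row and is counted as a new event on drug.

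GI perforation is a rare, acute outcome that the study is meant to describe on tofacitinib and, if feasible, to compare with bDMARDs. If an unknown share of its events are something else, neither the rate nor the ratio can be read as a statement about perforation.

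**Working it through.** **1. The code list.** The ARTIS row holds 27 codes: K22.3 (1); four each under K25, K26, K27 and K28 (16); K31.6 (1); K35.0 and K35.1 (2); four under K57 (4); K63.0, K63.1 and K63.2 (3). 1 + 16 + 1 + 2 + 4 + 3 = 27. Three of them, K31.6, K63.0 and K63.2, are fistula or abscess codes. The labels are an outside assumption, since the protocol prints codes only. Its own text does keep the concepts apart: the other registers' column for this endpoint has separate terms for intestinal abscess, intestinal fistula and intestinal perforation.

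**2. Overlap.** The serious infection list contains "K57.0, K57.2, K57.4, K57.8, K61, K63.0". Five of the 27 GI codes (K57.0, K57.2, K57.4, K57.8, K63.0) are therefore also serious infection codes. For K63.0 this agrees with its reading as an infection.

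**3. Position and incidence.** Set side by side, two rows name the main diagnosis and the GI row does not. Any position is the natural reading of that silence, though it is not an express rule. Section 9.3.2 follows patients from treatment start to each outcome and states no exclusion for earlier occurrences. Section 9.3.1 names several baseline histories but not GI perforation or fistula; that list is open-ended.

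**4. The cited PPV.** The figure of 89.1 to 100 cannot be reproduced, because the protocol gives no counts. It was obtained with another coding version, another list and another country. The earlier ARTIS studies named in Section 9.7.2 cover serious infections, PML and MACE, not GI perforation. Nothing quoted measures how often the present 27 codes mark a perforation.

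**5. What mixing does to a ratio.** Let p be the share of qualifying events in the comparator cohort that are perforations, R the true rate ratio for perforation, and F the rate ratio for the added events. Then

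observed ratio = p × R + (1 − p) × F.

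Take R = 2, the two-fold difference used for power in Section 9.5; the protocol gives no rate or effect for GI perforation. The values p = 0.891 and 0.85 borrow the lower ends of the two cited PPV ranges only as reference points. The values p = 0.70 and 0.50, and all values of F, are assumptions.

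| p | F = 1 | F = 2 | F = 3 |
|---|---|---|---|
| 1 | 2.00 | 2.00 | 2.00 |
| 0.891 | 1.89 | 2.00 | 2.11 |
| 0.85 | 1.85 | 2.00 | 2.15 |
| 0.70 | 1.70 | 2.00 | 2.30 |
| 0.50 | 1.50 | 2.00 | 2.50 |

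For example, 0.891 × 2 + 0.109 × 1 = 1.89 and 0.50 × 2 + 0.50 × 3 = 2.50. The ratio falls if F is below R, is unchanged if they are equal, and rises if F is above R.

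**The case against.** The strongest objection is that the definition is not final. Section 9.7.2 defers a harmonised algorithm to the SAP, and Appendix 2 says that outcome details will be agreed before each report. That lowers the weight of the point but does not remove it. Appendix 4 is the algorithm the protocol says ARTIS uses, and the lists to be harmonised with are wider still: beside abscess and fistula they include diverticulitis and gastrointestinal haemorrhage. Harmonising towards them would not bring the endpoint closer to perforation.

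That shared breadth also argues against simply cutting the ARTIS list, because Section 9.7.2 plans meta-analysis across registers. This stands, and so the present list should be kept beside a narrower one.

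The protocol is open about validity. It labels the PPV as a US ICD-9 result and says its own algorithms are not validated. A reader might infer that it claims the PPV for the ARTIS list; it does not. What remains is that the figure lends this list no support.

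The PML row also says only that a code is listed, so GI perforation is not the sole row without a position limit. A strict main-diagnosis rule could also lose true perforations coded second. Both points stand. Finally, an admission counting under both serious infection and GI perforation is not itself a fault, since endpoints are analysed separately and MI and MACE overlap by design.

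**Conclusion.** The point holds as a defect of definition. Followed as written, the row counts abscesses, and fistulas that predate treatment, as new perforations. The reported rate and any hazard ratio would be for a mixed outcome. This rests on the standard ICD-10 labels and on reading the row's silence as no position limit.

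A reader might infer that the mixing pulls any excess on tofacitinib towards no effect. The documents do not support a fixed direction. It holds only if the added events are less related to tofacitinib than perforation is. Section 7.1 calls serious infection an identified risk of tofacitinib, which bears on abscesses. Section 9.9 expects channeling of patients with more severe and longer disease, who may carry more old fistulas. Either could raise the tofacitinib rate instead.

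Nor can the size be given. The protocol states no GI perforation rate, code mix or PPV for its list, and 3 of 27 codes says nothing about the share of events. The range of 1.50 to 2.50 around a true ratio of 2 illustrates assumed inputs and is not an estimate.

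The hazard ratio is itself conditional: comparison is pending feasibility, and the Table III shell in Appendix 2 requires at least 5 events in both cohorts. The descriptive rate is affected in any case.

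**What to change.** In Appendix 4, and carried into the harmonised algorithm in the SAP:

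- Add a perforation-specific ARTIS definition that omits K31.6, K63.0 and K63.2 (27 − 3 = 24 codes) and requires that no listed code was recorded before the cohort index date. Apply it in all cohorts. Section 9.4.3 dates ICD-10 coding in the Patient Register from 1997, so a look-back is available.
- Report it beside the present 27-code list, kept and labelled as a broad definition for pooling with the other registers.
- State the diagnosis position. If a limit is wanted, use the wording of the serious infection and herpes zoster rows (main diagnosis, with contributory diagnoses when the main diagnosis is RA), as a sensitivity analysis rather than as the sole definition.
- In Section 9.7.2, say that the US ICD-9 PPV does not apply to the ARTIS list.

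The cost is Appendix 4 wording and one extra run. The strict definition will have somewhat fewer events, so it may miss the five-event minimum for a hazard ratio more often. Its rate would still be reported.

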### **9.8. Quality Control**

This study uses data existing within ARTIS. ARTIS works mainly with data from the SRQ, a quality of care register with several guidelines in place to monitor and maintain data quality. Physicians working with the SRQ have access to an online portal in which they can monitor all their patients and the information on them. Regional representatives encourage/remind the physicians to check the quality of the information by accessing the “Data Quality” section of the “Visit monitoring” tool: in this section a series of questions guide the doctor in checking the quality of the registered information of their patients. Moreover, the data coordinator of SRQ periodically check the quality of the data overall in the region.

### **9.9. Limitations of the Research Methods**

This study is designed to monitor the safety of tofacitinib within the clinical practice setting utilizing the ARTIS Register, a well-established Swedish-based rheumatology register. Despite the strengths of the register, data must be evaluated in light of their limitations. For example, consistent with most observational studies, the possibility of channeling and endpoint misclassification, are of concern in interpreting findings.

As a new therapy in the RA treatment armamentarium, it is possible that patients treated with tofacitinib will represent those with the most severe cases of disease, longer disease duration,

history of multiple failed RA therapies and physical comorbidities that place patients at risk for events. Biases resulting from channeling may present as increased rates of safety events of interest in the early phases of the study. Comparison to internal comparators may illuminate such channeling. Stratification on key indicators of disease severity, patient characteristics and past therapies can be done for contextualization. Trend analyses may be conducted to evaluate rates in tofacitinib patients over time.

The RA treatment landscape has evolved over time with the introduction of new therapies, treatment recommendations, and approaches to patient management. The rates of safety events of interest and their distribution among patient-types may have changed over time. The comparators in this study are not exclusively contemporaneous to tofacitinib treated patients. Analysis may be unable to identify or control for any changes in rates due to changes in the treatment landscape.

Event misclassification is of particular concern within the observational setting due to less stringent monitoring relative to clinical trials. While ARTIS has an established system to identify and capture endpoint data, all events cannot be fully verified via source documentation. Instead, linkage to national health care registers allows the register to obtain data on all safety events of interest (regardless of suspected causal relationship to the treatments), and on comparator cohorts, so that any potential risk increases can be evaluated in light of risks among patients and with other treatments, and the general Swedish population.

Certain patient characteristics which may influence VTE outcomes (e.g., smoking status, obesity and immobilisation), cannot be reliably captured, and thus may limit data interpretation. Inherited coagulation disorders encompass a broad range of conditions, and only a limited number of these can be reliably captured in the Swedish registers. While immobilisation cannot be captured in the Swedish registers, including inpatient care due to RA (i.e., RA as main diagnostic listing) will capture hospitalized patients who will be immobilized, and who will also be at a potentially higher risk for VTE (consensus guidelines recommend thromboprophylaxis for all admitted patients with inflammatory bowel disease (IBD) in the absence of contraindications). Additionally, some CV risk factors such as smoking status (as previously mentioned) and baseline total cholesterol/HDL ratio cannot be adequately captured within the Swedish registers, and thus will limit the assessment of the MACE and MI endpoints. For the outcome of lymphoma, the 3 main subtypes that can be adequately be captured in the Swedish registers are NHL, Hodgkin lymphoma and chronic lymphocytic leukemia (CLL). Other lymphoma subtypes that do not fit into these 3 main categories will not be captured in the study and thus may limit the assessment of this outcome.

This study will follow patients for a period of 7-years from therapy initiation. Conclusions may not be generalizable outside of the 7-year period since initiation of therapy.

#### **9.10. Other Aspects**

Not applicable

## **10. PROTECTION OF HUMAN SUBJECTS**

### **10.1. Patient Information**

This study involves data that exist in anonymized structured format and contain no patient personal information.

All parties will ensure protection of patient personal data and will not include patient names on any sponsor forms, reports, publications, or in any other disclosures, except where required by laws. In case of data transfer, Pfizer will maintain high standards of confidentiality and protection of patient personal data.

### **10.2. Patient Consent**

As this study involves anonymized structured data, which according to applicable legal requirements do not contain data subject to privacy laws, obtaining informed consent from patients by Pfizer is not required.

### **10.3. Patient Withdrawal**

Not applicable; analyses planned utilize data from secondary data sources that do not include patient identifiers.

### **10.4. Institutional Review Board (IRB)/Independent Ethics Committee (IEC)**

There must be prospective approval of the study protocol, protocol amendments, and other relevant documents (eg, informed consent forms if applicable) from the relevant IRBs/IECs. All correspondence with the IRB/IEC must be retained. Copies of IRB/IEC approvals must be forwarded to Pfizer.

This register-linkage database does not contain any patient identification information (eg, name), except for a unique number assigned for the purpose of linking files. This comparative safety study has been approved by the Ethics Committee in Stockholm (DNR: 2015/1844-31/2, renewed approval will be sought as needed for the duration of the study).

#### **10.4.1. Ethical Permits**

In accordance with Swedish law, non-interventional studies of register-based data (including “quality of care” registers such as SRQ/ARTIS) do not usually require informed consent by the individual study subjects. Instead, regional ethics committees are mandated to provide permission for such studies, after weighing the subjects’ potential benefit from the research against the potential risks to the subjects’ personal privacy. ARTIS has ethical approval for the studies described in this protocol as outlined above, but is subject to strict rules and regulations regarding the maintenance, analysis and reporting of personal data. Patient consent is not required for this study as data already exist within ARTIS register.

